PROTOCOL TITLE: Efficacy of a Coupler-Based Fitting Approach for Experienced Users Receiving Replacement Hearing Aids

PRINCIPAL INVESTIGATOR: [name], Au.D., Ph.D.

VERSION NUMBER AND DATE: Version 10, June 10, 2022

SPONSOR/FUNDING SOURCE: VA RR&D Merit Review C2777-R

Purpose

The overarching purpose of this project is to develop an accurate coupler-based fitting model for experienced hearing-aid users obtaining replacement hearing aids of any style that will result in positive patient outcomes while mitigating a face-to-face fitting visit.

The proposed project addresses three aims:

Specific Aim 1. Develop vent correction factors for testbox fittings of in-the-ear (ITE) and traditional behind the ear (BTE) with custom earmold hearing aids, which will be used to evaluate the real ear to complete difference (RECD)-fitting approach in a sample of experienced users receiving replacement hearing aids. Hypothesis 1a. RECD coupler-based fittings will accurately meet prescriptive targets and expected aided audibility for ITE and traditional BTE styles. Hypothesis 1b. Subjective outcomes from RECD coupler-based fittings will meet or exceed published norms.

Specific Aim 2. Develop correction factors for RECD coupler-based fittings of hearing aids with non-custom coupling (i.e., mini-BTEs with slim tubing and noncustom open canal coupling—open fits). Hypothesis 2. Correction factors will be developed to account for RECD coupler-based fittings with open canals.

Specific Aim 3. To determine if the open-fit RECD-fitting approach is equivalent to the standard of care (SoC) open-fit fitting approach. Hypothesis 3a. Derived REARs from open-fit RECD-fittings will accurately meet prescriptive targets and expected aided audibility and will be equivalent to in situ REARs in SoC fittings of open-fit styles. Hypothesis 3b. The subjective outcomes will not significantly differ between the experimental RECD-fitting group and the SoC group for open-fit styles.

Background and Significance

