short, the test box reference microphone will be calibrated. The probe tube will be inserted 25-27 mm from the intertragal notch in order to ensure placement within approximately 2-5 mm from the eardrum. The foam insert will be placed in the ear canal and care will be taken not move the probe tube during insertion. The RECD transducer will be coupled to the foam insert and the real-ear response will be obtained. The difference between the HA-1 coupler and real ear response is the measured RECD. Clinical application of the proposed model assumes all necessary pre-fitting procedures (e.g. earmold impression, tubing length, RECD) are completed at this session.

Session 2: The Testbox Fitting 'Visit'. Within five business days of receipt of the replacement hearing aids, the testbox fitting 'visit' will occur. The participants will **not** be present during the fitting. The vent size of each hearing aid will be measured. For both groups, the BTE earmold/ITE hearing aid will be attached to the 0.4cc coupler with putty ensuring that the eartip is flush against the opening of coupler and the vent sealed, as is standard with this procedure. The right and left hearing aids will be programmed separately to the NAL-NL2 prescription generated from the Verifit 2 using the measured RECD from Session 1 of each ear. The derived REAR of the hearing aids will be verified to the 50-, 65-, and 75-dB SPL prescriptive targets generated by the Verifit 2 system using the speechmap stimulus. The criterion for an appropriate fitting would be ± 3 dB between the output and the prescriptive target from 250 Hz to the frequency in which the unaided threshold crossed the 65-dB SPL target. We will then apply the refined vent size correction factor we previously determined. The real ear aided response (REAR85) will be measured using an 85-dB SPL swept pure-tone to ensure that the maximum output of the hearing aids does not exceed the predicted uncomfortable loudness levels of the participant (feedback manager deactivated during this measurement only). The programming options will be optimized based on the information obtained on the intake form (Appendix). After programming and verification, the hearing aids will be mailed to the patient along with the manufacturer brochure and programming report from the manufacturer software. A signature will be required to accept the delivery and the delivery will be tracked.

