Study 1 Power Analysis. The primary outcome of interest is based on fitting accuracy of each ear (i.e., deviation of REAR from prescriptive target across frequency). A power analysis for a repeated measure ANOVA with an effect size $\eta^2 = 0.10$, power ($1-\beta$) = 0.80, and $\alpha = 0.05$ requires a sample size of 100 ears (total of 50 participants) over the two groups. A small effect size is expected, as a small effect size was found in the preliminary data ($\eta^2 = 0.10$). Considering 15% attrition, then 8 additional participants will be needed ($N = 58$) resulting in 29 participants per group.

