Study 1 Data Analysis Plan. A generalized linear model will be applied to examine fitting accuracy. This analysis will examine differences (in dB SPL) for in situ REAR (based on testbox fittings) across frequency between the groups relative to the prescription. Because it is expected that differences within the two ears of the same subject will be smaller than differences across subjects, inclusion of both ears in the same analysis may over inflate the statistical power. However, it is also of interest to ensure that all data are considered. Therefore, we propose to complete separate analyses for the left and right ear, even though we expect the pattern of results to be very similar for each ear. These analyses will determine (1) in situ REARs of the testbox fittings matched the prescription within each group, and (2) if there was an effect of fitting accuracy as a function of style. A generalized linear model will be conducted to compare the expected (from prescription) and actual aided SII within and between groups. Finally, separate mixed model repeated measures ANOVA will be applied to examine group differences among the outcome measure subscales (i.e., SADL subscales, IOI-HA items/subscales, and for the APHAB subscales) to examine differences in outcomes between groups and between current hearing aid fittings and the replacement testbox fittings. For the COSI, the percentage of 'better' and 'much better' responses and the average of the final ability will be calculated across goals and compared between groups via a paired-sample t-test. The subjective outcomes of replacement hearing aids (Session 3) from testbox fittings will also be compared to normative data for each group by comparing our mean, standard deviation, and sample size to those same variables from the published outcome respectively via a Welch test. This will inform whether our outcomes for testbox fittings of replacement hearing aids from each group were consistent with the published norms or not. For the IOI-HA, the IOI-HA norms from the VA ROES DALC database that contains over 100,000 IOI-HA records will be used. In the same fashion, we can select IOI-HA norms from ROES by based on degree of hearing loss and hearing aid style. A

logistic regression also will be conducted to examine if the proportion of responses differ between the groups on the specific telephone and exit survey items of interest.

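### Study 1 plans to determine that testbox fittings matched the prescription from a model of differences with no margin, which cannot show agreement

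*Combined protocol and SAP*

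**What the plan says.** Hypothesis 1a (Purpose, Specific Aim 1) reads: "RECD coupler-based fittings will accurately meet prescriptive targets and expected aided audibility for ITE and traditional BTE styles". The Study 1 Power Analysis makes this the main endpoint: "The primary outcome of interest is based on fitting accuracy of each ear (i.e., deviation of REAR from prescriptive target across frequency". The sample size there is for a repeated-measures ANOVA with η² = 0.10, α = 0.05 and power 0.80, and "requires a sample size of 100 ears (total of 50 participants) over the two groups". With 15% attrition the plan enrols 58, or 29 per group.

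The Study 1 Data Analysis Plan applies a generalized linear model to the Session 3 in situ responses: "This analysis will examine differences (in dB SPL) for in situ REAR (based on testbox fittings) across frequency between the groups relative to the prescription". To avoid overstating power from paired ears, it adds that "we propose to complete separate analyses for the left and right ear". On the within-style question it then says: "These analyses will determine (1) in situ REARs of the testbox fittings matched the prescription within each group".

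No limit, interval or proportion is attached to the word matched. A tolerance does appear elsewhere. Under Study Interventions, Study 1, Session 2, the testbox fitting is held to ±3 dB: "The criterion for an appropriate fitting would be ± 3 dB between the output and the prescriptive target". That governs programming in the sealed coupler, and the vent correction is applied afterwards. The analysis plan does not refer to it. Background section 1c mentions ±5 dB agreement between measured and derived responses in earlier research, without adopting it as a margin.

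**The concern.** A claim that fittings meet target needs evidence that the deviation is small. Testing whether the mean deviation differs from zero does not supply that evidence, and without a margin it can mislead in two ways. If deviations vary widely between ears, a real miss may be non-significant and could be reported as a match because the method was imprecise. If they vary little, a deviation well inside ±3 dB may be significant and could be reported as a failure to match.

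The power statement does not close the gap. It concerns an ANOVA over both groups, whereas this conclusion is drawn within one style and, after the split by side, from about 25 ears at a time.

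The project aims to make a face-to-face fitting visit unnecessary, so whether the fittings matched target carries much of the Study 1 conclusion. The Study 3 Data Analysis section says it will follow a similar plan for its fitting-accuracy variables, so the gap carries forward.

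**Working it through.** **1. The plan's own figure.** η² = 0.10 gives f = √(0.10/0.90) = 0.333. A plain two-group comparison at α = 0.05 and power 0.80 needs 73 ears in total. A repeated effect with four levels and noncentrality N·f² gives exactly 100. The plan states neither the number of levels, nor their correlation, nor the effect tested, so 100 ears can be reached but not confirmed. All of these calculations address detection of a difference; none gives the chance of showing a match. For attrition, 50 × 1.15 = 57.5, rounded to 58, and 58/2 = 29 per group.

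**2. Ears available for the within-style question.** 50 evaluable participants / 2 styles = 25 participants. With sides analysed separately, that is 25 ears per style per analysis.

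**3. Illustration: test of zero mean deviation.** Two-sided one-sample t, n = 25, α = 0.05 (sidedness is not stated; two-sided is assumed), critical value t(24) = 2.064, noncentrality δ = √25 × (true deviation / SD). The documents give no between-ear SD, so every SD is an assumption, and 0.5 SD is a chosen example.

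| True deviation | SD (dB) | δ | Non-significant | Significant |
|---|---|---|---|---|
| 0.5 SD | any | 2.50 | 33% | 67% |
| 3 dB | 4 | 3.75 | 5% | 95% |
| 3 dB | 5 | 3.00 | 18% | 82% |
| 3 dB | 6 | 2.50 | 33% | 67% |
| 3 dB | 7 | 2.14 | 46% | 54% |
| 1 dB | 2 | 2.50 | 33% | 67% |
| 1 dB | 3 | 1.67 | 64% | 36% |

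If all 29 enrolled per style were evaluable, the 33% for a 0.5-SD deviation falls to 26%. At SD 3 dB a 3 dB miss is non-significant only 0.2% of the time.

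**4. Illustration: margin rule.** Pass if the 90% interval, mean ± 1.711 × s/√25, lies inside ±3 dB (simulated, one mean, n = 25).

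| SD (dB) | Pass, true 0 dB | Pass, true 3 dB |
|---|---|---|
| 3 | >0.99 | 0.05 |
| 4 | 0.95 | 0.05 |
| 5 | 0.80 | 0.05 |
| 6 | 0.57 | 0.05 |

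**5. Limits of a rule on the mean.** If deviations are normal with mean zero, the share of ears within ±3 dB is 2Φ(3/SD) − 1. That is 55% at SD 4 and 45% at SD 5, although the mean rule passes with probability 0.95 and 0.80.

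**6. Combining tests.** Suppose each of 6 frequencies (assumed) in both ears must pass, making 12 tests per style, with true deviation zero and a common correlation between 0 and 0.8 (assumed). The chance that all pass is about 0.57 to 0.82 at SD 4 and 0.06 to 0.43 at SD 5.

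**The case against.** A reader might infer that the plan defines a non-significant deviation as a match. It does not: no p-value rule is written for this conclusion, and the model is said to examine differences in dB, so estimates could be read against ±3 dB or ±5 dB. This stands, and the defect is the absence of a criterion. It does not remove the point, because the text promises a determination and states no other way to reach one.

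A reader might also take one in three as the trial's error rate. The documents do not support that. The effect size and every SD are assumed, and the planned model spans frequencies and is run for two ears, so its operating characteristics will differ. The figures show the direction of the problem and its possible size.

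Nor is ±3 dB already the in situ margin. It is a testbox programming criterion applied before the vent correction, and the ±5 dB in the background describes agreement between measured and derived responses. Carrying either one to the Session 3 result needs justification from the sponsor.

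Finally, a rule on the signed mean lets overshoots and undershoots cancel, while the plan defines its outcome as accuracy of each ear. This objection is sound and shapes the fix.

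**Conclusion.** The point holds as a missing criterion for agreement on the primary outcome of Study 1. The stated method cannot establish that in situ responses matched the prescription within a style, and the stated 0.80 power does not refer to that conclusion. If non-significance were read as a match, a true 3 dB miss could pass unnoticed about 5% to 46% of the time at SD 4 to 7 dB. If significance were read as failure, a 1 dB deviation could fail 67% of the time at SD 2 dB. These sizes rest on a single-mean t-test, 25 ears per style per side and assumed SDs. The documents establish the absence of a rule; they do not show that a wrong rule was adopted. The change should be made before the data are analysed.

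**What to change.** In the Study 1 Data Analysis Plan:

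- State that a non-significant difference from zero will not be read as a match.
- Judge Hypothesis 1a for each style by the 90% confidence interval for mean in situ REAR minus target, against a pre-specified margin. The plan's ±3 dB is the natural candidate. The sponsor should justify carrying a testbox, pre-vent-correction criterion to the in situ result, or justify another margin.
- Report the proportion of ears within that tolerance, or the mean absolute deviation, so that accuracy of each ear is shown.
- Name the input level used, and say how frequencies and ears are combined: one summary across frequency, or all must pass.

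In the Study 1 Power Analysis, state that the 0.80 is for the ANOVA over the two groups and not for showing a match within a style. Add the chance of meeting the chosen rule at about 25 ears per style for a stated SD.

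The cost is wording only, with the same data and visits. The downside is that, with a ±3 dB margin, Hypothesis 1a may be inconclusive at a between-ear SD above about 5 dB for a single summary, or from about 4 dB if every frequency and ear must pass.

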In addition to the longer than desired wait time for the fitting appointment, Veterans and their family members also are inconvenienced with travel to the medical center. Many service-connected Veterans, however, are compensated for travel costs. Travel compensation costs for just the Mountain Home VA Medical Center last year (for all visits, not just audiology) totaled over \$8 million. Once the Veteran arrives at the medical center, s/he is often burdened with parking, navigating to the clinic, or finding a wheelchair or escort to facilitate navigation to the clinic. An efficacious RECD-based fitting approach that could bypass patient travel (and associated costs), a face-to-face appointment, and long wait-times for appointments would be highly desirable for many Veterans receiving replacement hearing aids and would have a significant impact on Veteran-Centric outcomes and VA resources. This project will evaluate an experimental coupler-based fitting procedures designed to greatly improve the efficiency of hearing-aid delivery to experienced hearing-aid wearers. Because the proposed model assumes that tubing length and earmold impressions (when applicable), as well as RECD measures are completed during the initial fitting, no visit is necessary for replacement hearing aid services.

Design

This project contains three separate experiments, one experiment for each aim.

Study 1 will use a quasi-experimental design. Two groups of experienced hearing aid users will receive replacement hearing aids using an experimental service-delivery approach. One group will be receiving replacement behind-the-ear (BTE) hearing aid style and the other group will be receiving replacement in-the-ear (ITS) hearing aids styles. The outcomes of the new hearing aids of both groups will be compared to the previous hearing aids and between groups.

Study 2 will use a quasi-experimental design. One group of subjects will receive 12 mini-BTE hearing-aid fittings (with both open and closed coupling) in one ear. The ears across subjects will be counter-balanced. Hearing aids from 3 different manufacturers and configurations will be fitted using a randomly assigned simulated audiogram. The output of these fittings will inform correction factors for hearing aid fitted in Study 3.

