Participants may directly benefit from this protocol. They all will receive a comprehensive audiologic evaluation and those results will be placed in their medical record. For those in Study 1 and 3, their current hearing aids will be evaluated to ensure proper function and best fit. If in need of repair, maintenance, or adjustment, these will be made. Their replacement hearing aids will be carefully fitted and verified to best practices and they will receive close follow-up regarding them. They may enjoy the benefit of obtaining hearing aids without having to come into the clinic for a face-to-face visit (experimental groups only). If the results between the SoC and experimental groups are equivalent, then this study would provide an evidence-based, RECD fitting approach that will improve Veteran-Centric care. Specifically, the RECD-based delivery model reduces the number of visits required to fit a replacement hearing aid compared to the SoC delivery model and, therefore, should result in greater patient satisfaction and reduced costs. In addition, the reduction in the number of clinic visits for established hearing aid patients may produce a reduction in wait times (greater access to care) for new patients seeking audiology services. The risks to participants is less than minimal and the anticipated benefits outweigh the minimal risk.

Selection of Subjects

Study 1 and Study 3: Inclusion Criteria:

Participants will be included in the study if the following criteria are met:

1. aged 18-85 years
2. experienced hearing-aid users who are obtaining replacement VA-issued hearing aids of the same style as their current hearing aids
3. competent hearing aid skills as demonstrated via the checklist (See appendix)
4. no more than a moderate sensorineural hearing loss (defined as less than or equal to 60 dB HL pure-tone average at 500, 1000, and 2000 Hz AU)
5. symmetrical hearing between the ears as defined as no more than a 20 dB difference in pure-tone thresholds at two consecutive frequencies
6. >/=50% word-recognition abilities in quiet as measured during the diagnostic audiologic evaluation

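### Study 1's BTE-versus-ITE comparisons are between non-randomised groups and carry no hearing-loss term, so they may be confounded by degree of loss, which Session 1 already measures

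*Combined protocol and SAP*

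**What the plan says.** **Design.** The Design section calls Study 1 quasi-experimental and defines the groups by device: "One group will be receiving replacement behind-the-ear (BTE) hearing aid style and the other group will be receiving replacement in-the-ear (ITS) hearing aids styles". Inclusion criterion 2 (Selection of Subjects) admits "experienced hearing-aid users who are obtaining replacement VA-issued hearing aids of the same style as their current hearing aids", so group membership is the style already worn.

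**Hearing loss.** Inclusion criterion 4 caps the pure-tone average over 500, 1000 and 2000 Hz at 60 dB HL and states no lower limit. No matching or stratification by loss is described. Session 1 includes pure-tone audiometry, with each ear tested separately.

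**Analysis.** The Design section promises that "The outcomes of the new hearing aids of both groups will be compared to the previous hearing aids and between groups". In the Study 1 Data Analysis Plan, the second aim of the REAR analysis is to see "if there was an effect of fitting accuracy as a function of style". The plan also compares the groups on aided SII and on the SADL, IOI-HA and APHAB subscales. No covariate is named in any of these models. Degree of loss enters the Study 1 analysis in one place only: IOI-HA norms can be selected "based on degree of hearing loss and hearing aid style". That step concerns the comparison with norms, not BTE against ITE.

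**The concern.** People who wear custom BTE and ITE aids chose, or were given, those styles for reasons that may include their hearing. Nothing in the design makes the two groups comparable on loss, and about 25 per group is too few to count on balance by luck.

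The plan itself treats loss as potentially relevant. It allows norms to be chosen by degree of loss, and the Study 2 Data Analysis section lets the correction model be adjusted for hearing loss if needed.

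If loss differs between the styles and also relates to the error around target or to self-report, an unadjusted BTE-versus-ITE difference mixes the two. It could be read as the coupler-based method, or its vent correction, working less well in one style. A real style difference could equally be hidden.

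**Working it through.** The plan gives no figure on this point, so there is none to reproduce. Only the group size and the planning effect size come from the documents.

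**Inputs**
- From the Study 1 Power Analysis: 50 participants over two groups, so n = 25 per group; η² = 0.10; α = 0.05. Left and right ears are analysed separately, so each model has 50 independent units.
- Assumed, because the documents are silent: D, the difference between groups in mean pure-tone average in within-group SDs (0 to 1.0); and r, the within-group correlation of pure-tone average with outcome (0.2 to 0.4).

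**Step 1: false-positive rate without adjustment.** With no true style effect, the spurious standardised difference is d = r × D. A two-sample t test on 48 df has noncentrality d × √(n/2) = 3.536 × r × D. For r = 0.4 and D = 1.0 this is 1.414; for r = 0.3 and D = 0.8 it is 0.849. Two-sided rejection rates at nominal 5%:

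| r | D = 0 | D = 0.5 | D = 0.8 | D = 1.0 |
|---|---|---|---|---|
| 0.2 | 5.0% | 6.4% | 8.6% | 10.7% |
| 0.3 | 5.0% | 8.2% | 13.2% | 18.0% |
| 0.4 | 5.0% | 10.7% | 19.8% | 28.3% |

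A simulation of 20,000 trials per cell for D of 0.5 to 1.0 gave close agreement (for example 13.0% at r = 0.3, D = 0.8). The covariate-adjusted test stayed at 4.9% to 5.2%. This is a simplified single-score test, not the planned repeated-measures model.

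**Step 2: what adjustment costs.** Take f² = 0.10/0.90 = 1/9, so λ = 50/9 = 5.556. On 1 and 48 df the power is 0.637. A useless, balanced covariate gives 0.636. In general the adjusted λ is 5.556 / [(1 − r²)(1 + D²/4)] on 1 and 47 df:
- D = 0.8, r = 0.3: 5.556 / (0.91 × 1.16) = 5.263, power 0.613.
- D = 1.0, r = 0.2: 5.556 / (0.96 × 1.25) = 4.630, power 0.559.
- D = 0.8, r = 0.4: 5.556 / (0.84 × 1.16) = 5.702, power 0.648.

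Power can therefore fall or rise, depending on imbalance and correlation.

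**Step 3: which term is needed.** For a participant scored at two times, a term β × PTA appears in both scores and drops out of their difference. The group-by-time contrast is the difference in mean change, so a main effect of PTA leaves it unchanged when the data are balanced. In one simulated data set the contrast was 0.620 with and without the PTA main effect. The same algebra holds for group-by-frequency. Only PTA-by-time or PTA-by-frequency terms reach these contrasts.

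**The case against.** **No imbalance is shown.** This is right. The documents do not show that BTE and ITE users differ in loss, or that loss predicts error around target. With D = 0 the false-positive rate is 5%. A reader might infer that a style effect cannot be told from a hearing-loss effect; the documents support only that it may be confounded.

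**The outcomes are already indexed to loss.** REAR is scored against a prescription derived from each person's thresholds, SII is expected against actual, and each aid is first programmed in the coupler to within 3 dB of target. This removes the effect of loss on the target. It does not remove any dependence of the remaining error on loss, and the upper frequency limit of the 3 dB criterion is itself set by the unaided threshold.

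**Self-report has a baseline.** Current-aid scores are collected at Session 1, and the mixed models compare current with replacement fittings. A stable effect of loss cancels from that change. It does not cancel from a between-group comparison of scores, and change itself may depend on loss.

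**Only secondary contrasts are touched.** Hypotheses 1a and 1b concern meeting targets and norms, and can be judged within each style. A reader might also infer that the style contrast is what the sample size was built on. The power section names a repeated-measures ANOVA over the two groups without saying which term is powered.

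**The groups might be called random.** Costs and/or Payments to Subjects refers to random assignments for Studies 1 and 3, but in the context of payments. That does not fit how the Study 1 groups are formed.

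**Conclusion.** The point holds as a possible confounding of Study 1's between-style contrasts: the style question for REAR deviation and the between-group comparisons of SII and self-report. Under the assumed range (imbalance 0 to 1.0 SD, r of 0.2 to 0.4, 25 per group, no true style effect), the unadjusted false-positive rate is 5% to 28%. The threshold-derived target and the current-aid baseline probably put the actual exposure below what the same imbalance would do to an unscaled score, but by how much cannot be determined from the documents.

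The point does not show that bias is present and does not disturb the within-style results. Nor would adjustment turn the contrast into the causal effect of style. One three-frequency average leaves age, vent size and audiogram slope uncontrolled, and it relies on the groups overlapping in loss.

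**What to change.** In the Study 1 between-style models for REAR deviation, SII, SADL, IOI-HA and APHAB:
- Add the Session 1 pure-tone average (500, 1000, 2000 Hz): ear-specific for REAR and SII, the mean of both ears for self-report.
- Include PTA-by-frequency in the REAR model and PTA-by-time in the self-report models.
- Report unadjusted and adjusted contrasts side by side, with the distribution and overlap of PTA in the two groups.
- Describe the adjusted result as a style difference adjusted for degree of loss.

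The COSI and telephone/exit-survey comparisons are also unadjusted. If they are kept as between-style tests, the report should say so.

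**Cost.** Analysis-plan wording only, best settled before outcomes are analysed; no new data, visits or participants. Each added parameter uses one degree of freedom; with frequency as a categorical factor, the interaction uses one for every frequency beyond the first. Precision may fall if the groups differ in loss, as the power figures of 0.613 and 0.559 against 0.637 show.
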